 - o R01 DA Screen form
 - o RO1 DA Tobacco Smoking Session Day and Exposure form 4.14.16
 - o R01 DA 7 Day Self-Report 4.14.16
 - 11 R01 Appendix K. Saliva Test Procedure [name] 1.3.13

Graduate and Research Affairs

Division of Research Affairs San Diego State University [name] Phone: [name]

Sincerely,

[name]

Chair, Institutional Review Board

A research project to determine the differential effects of waterpipe (WP) smoking practices on biomarkers of toxicants and carcinogens related to waterpipe tobacco smoking in naturalistic settings – urine analyses by Drs. [name] and [name] laboratories. (Table 1)

We will compare exhaled CO, and urinary levels of cotinine, NNAL, SPMA, and 1-HOP in first void WP smoker urine samples the morning of, and the morning after a WP smoking session across 3 configurations, as shown in Table 1

Study Design and Target Population

We will employ a repeated measures design. We will recruit a sample of 50 adult male and female exclusive WP smokers and a control sample of 25 male and female non-smokers. Participants will be recruited via intercept interviews from San Diego County, CA communities. Over a 4-week study period, WP smokers will smoke one WP tobacco head (10g) of *Starbuzz* during 3 separate sessions with a 7-day washout period before each session in their

Table 1. Three waterpipe (WP) smoking sessions.				
3 WP smoking Confiurations at home	Heat Source	WP Jar Contents		
WP smoking session 1	Charcoal ²	Water 4		
WP smoking session 2	Charcoal	Ice cubes 5		
Training for session 3 ¹	Electric ³	Water		
WP smoking session 3	Electric	Water		

- ¹ Smokers will be trained on using the Electric WP head
- ² Quick-light charcoal *Three Kings* (40mm)
- ³ Charcoal-free electrically heated WP head
- ⁴ Room temperature drinking water in the WP jar
- ⁵ Adding ice cubes in the water in the WP jar For all 3 configurations, flavored WP tobacco, *Starbuzz* (10g), Double Apple flavor will be smoked at home, Aluminum sheet (9x9cm) will be used to cover the WP head, volume of water & ice cubes will be standardized.

home in a naturalistic setting: Week 1-Session 1, WP smokers will smoke using 1 quick-light charcoal and room temperature water in the WP jar, Week 2-Session 2, WP smokers will smoke using 1 quick-light charcoal but adding ice cubes to the water in the WP jar, Week 3-Training for session 3, RAs will train participants on how to use a charcoal-free electrically heated WP head to heat the tobacco, and Week 4-Session 3, WP smokers will smoke WP tobacco without charcoal using the electric WP head and room temperature water. We will collect a) Tobacco Use History; b) 4-week Tobacco Use and Exposure Diaries; c) WP Smoking Session Day and Exposure Form; d) CO exposure: Micro+Smokerlyzer® CO monitor will be used for exhaled CO two minutes pre and post each smoking session; and e) 6 first morning urine samples: pre and post the 3 sessions to measure urinary cotinine, NNAL, 1-HOP, and SPMA. We will measure urinary Furan-BDA-NAL in WP smokers who smoke WP tobacco as commonly practiced using quick-light charcoal and room temperature water in the WP jar (urine samples from Session1).

Inclusion Criteria for Participants

Adult waterpipe smoker: A male or female, 18 years or older, who smokes WP tobacco exclusively, smokes at least 1 WP head per month, and smokes at least 1 WP head per WP smoking session, smokes WP at home, agrees to smoke *Starbuzz* WP tobacco, and lives in a 'smoker home'. Adult non-smoker: A male or female, 18 years or older, who lives in a 'non-smoker home'.

Inclusion Criteria for Homes

A Smoker Home: is a home in which residents have smoked WP tobacco exclusively indoors/outdoors at least in the last month. A Non-smoker Home: is a home where to the knowledge of the residents no smokers have lived in and no visitors had smoked indoors/outdoors in the past month, and where a potential nonsmoker participant who has not been exposed to any secondhand smoke at least in the last month resided full-time.

Exclusion Criteria

Adults with major physical/psychiatric illnesses that are judged by the research assistants (RAs) to interfere with ability to give informed consent or to successfully complete an interview will not be included in the study. Daily WP smokers will be excluded because they may not be able to adhere to the wash-out periods before the 3 WP sessions. Pregnant women are also excluded.

Screening Potential Participants

The PI, study coordinator (SC), RAs and volunteering student interns will take part in all phases of the study. We have a collaborative relationship with SDSU internship faculty advisors. Potential participants will be approached at random in the community by the RAs accompanied by interns, and will obtain a verbal consent to complete a brief voluntary screening form which will be used to recruit individuals and determine their initial eligibility to participate in a SDSU research study. The PI will work closely with the SC and RAs to qualify participants. The RAs will contact initially qualified potential participants by phone and further determine their qualification by completing an eligibility checklist of inclusion and exclusion criteria. Qualified potential participants will be invited for an Office Visit at our research center for enrollment in the study.

The 4-Week Study period: comprised of 3 WP smoking sessions & 7-day activities per session (Table 2)

Waterpipe Smoking Session 1

Day 1 - Office Visit: The Office Visit is expected to take between 60 and 90 minutes. Trained by the PI, the SC and RAs will explain the 7-day study period activities for the 3 smoking sessions and consent form, answer all questions, and obtain a signed consent form. Thereafter, the RAs will give a saliva test to nonsmokers; interview participants face-to-

Table 6. Forms and measures for the 7-Day D	ata Colle	ction S	chedul	e for eacl	h of the	3 smoki	ng sessio	ns.
	Office visit			phone call 1		phone call 2	Home visit 1	Home visit 2
	Day 1	Day 2	Day 3	Day 4	Day 5	Day 6	Day 7	Day 8
Waterpipe Smoking Session Day							X	
Study Protocol and Consent Form	Х							
To bacco Use History Questionnaire	Х							
7-Day 24 hour Tobacco Use Diary	Х	Х	Х	Х	Х	X	Х	Х
7-Day 24 hour Tobacco Exposure Diary	Х	Х	Х	X	Х	X	Х	X
WP Smoking Session Day & Exposure Form							Х	
Provide First Morning Urine Samples							Х	Х
RAs Measure CO in exhaled breath							Х	
Illnesses & Medical Care History Form								X
RAs pick up urine samples							Х	X

face using the Tobacco Use History Questionnaire; explain how to complete the diaries on a daily basis; explain the urine collection protocol (2 first morning urine samples/smoking session); provide each participant with 2 coded empty urine cups (no names on urine cups and forms), gloves, 2 zip-lock bags/urine cup; ask participants to store the double sealed urine samples once obtained in his/her personal refrigerator (freezer section) until pickup by RAs the next day. Arrange for the smoking session and home visit on day 7 of the first week study period. The PI and SC will accompany the RAs to their first two homes (more if needed) for hands-on training for data collection. Wash-out period: smokers will abstain from smoking and exposure to any tobacco smoke for 7 days prior to each smoking session. WP smokers will choose a WP smoking day to start the 4-week study period; the RAs will coordinate the Office Visit accordingly. Non-smokers will choose any day to provide 2 first urine samples on two consecutive days. Saliva Test: Trained by the PI, the RAs will use NicAlert to validate non-smoking status, and as a bogus pipeline technique, which we used successfully in our previous studies. NicAlert, a commercial semi-quantitative instant saliva cotinine test, is accurate and valid with high sensitivity (93-100%) and specificity (95-96%) Non-smoking participants will be informed about the purpose of the NicAlert test during the informed consent process. (Appendix K. Saliva Test Procedure) Days 2 - 6: The RAs will contact participants by phone on the 4th day to confirm adherence to the 7-wash-out period and diaries, and on the 6th day to remind participants to collect the first morning urine sample on day 7, and to arrange for a home visit for the first WP smoking session. Day 7: Waterpipe smoking session 1. WP smokers will provide one first morning urine sample and store it in their refrigerator (freezer section). Participants from our previous WP studies stored their urine samples, double bagged in their refrigerator. WP smokers will smoke WP tobacco (10 grams) as they normally do using charcoal and room temperature water in the water jar. The RAs will collect expired CO levels 2 minutes before and 2 minutes after concluding smoking. Day 8: Participants will provide a first morning urine sample. The RAs will pick up the 2 urine samples (frozen), place them in a cooler (to transfer them to our research center laboratory for aliquoting and storage in a freezer at -20°C to be sent out for analyses); pick up the diaries and Waterpipe Smoking Session Day and Exposure From, arrange for the 2nd WP smoking session home visit, provide forms, urine cups package for week 2 of the study.

Waterpipe Smoking Session 2. The 7-Day study activities: Days 1 through 7 are similar to session 1 with the exception that the RAs will add one tray of ice cubes and water in the WP jar. The RAs will arrange for a training session to use the charcoal-free electrically heated WP head.

Waterpipe Smoking Session 3. The 7-Day study activities: *Training for session 3.* Any day during the third week, the RAs will arrange to visit the participants to train them on the charcoal-free electrically heated WP head, and arrange for the 3rd smoking session using the electric head. *Smoking session 3*. Days 1 through 7 are similar to session 1 using room temperature water in the WP jar, however using the charcoal-free electrically heated WP head instead of using charcoal. During the last visit, the day after the 3rd smoking session, the RAs will interview participants to complete the *Illnesses and Health Care History Form* (completed during the last day of the study period to avoid biasing smoking behavior), pick up the final urine samples, thank the participants and inform them that they will receive a check from SDSU in the amount of \$250 by mail.

Standardized Setting of the Waterpipe Device, Smoking Protocol, Waterpipe Tobacco and Charcoal

To reduce variance of factors extraneous to our configurations of WP smoking practices, we will standardize setting the WP device, aluminum foil, and amount, type and brand of WP tobacco and quick-light charcoal. We will determine and standardize the volume and commercial brand of drinking water to be placed in the WP jar, and volume of water and added ice cubes to be standardized.

Waterpipe Device. We will purchase 10 new unused WPs similar in specification to the Battelle Research-grade WP: 2L glass water jar, 28.6 cm length of body. All WPs will be the same size, style, and brand. In the kitchen of the participants, before and after each use, the RAs will thoroughly clean the stem and glass jar with soap and water between sessions and between participants. Three new hoses will be used for each smoker.

Smoking Protocol. During each WP smoking session, participants will be asked to smoke one WP tobacco head at their home as they normally do, not to share their WP with other smokers nor be in the presence of another smoker. WP smokers usually smoke 1 WP head per smoking session, ranging 30-60 minutes per session. At home of the participants, the RAs will set up the WP following a standardized protocol. Briefly, the RAs, wearing gloves at all times, will place room temperature commercial drinking water in the WP jar for sessions 1 and 3, and one tray of ice cubes and a standardized volume of water for session 2. The RAs will weight (using an analytical balance) and load one head of WP tobacco (10 gram Two Apples flavor, *Starbuzz* brand, U.S.), and cover it with a single (9x9 cm) aluminum sheet (manufacturer preperforated punch pattern). Using a portable lighter, the RAs will light a single quick-light charcoal (40 mm, *Three Kings* brand, Holland), and place it on the loaded WP head. At the conclusion of the smoking session, the RAs will weigh the remaining tobacco and charcoal, and complete the WP session observation form, such as length of time smoking, etc.

Waterpipe Tobacco Protocol and Brand - Starbuzz: All smokers will smoke the WP brand Starbuzz during the 3 WP sessions. We will purchase for each participant one package of Starbuzz tobacco to be used for the 3 smoking sessions and the training session. Following opening the package for session 1, the RAs will place the package in a sealed Ziploc bag and ask the participant to store it in a cabinet at room temperature and away from any direct sunlight until use the following smoking session. The majority of WP smokers use flavored WP tobacco Maassel (Table 2). We identified Starbuzz, a flavored WP tobacco brand, that is manufactured in the U.S. and is popular and accessible to WP smoker consumers based on: (1) a search of 'online vendors' such as hookah-shisha.com, hookahwholesalers.com, thehookah.com, and Amazon.com who provide a customer review section for WP tobacco products; (2) a survey of point-of-sale display of the most frequent WP tobacco brands in 6 Middle Eastern markets and smoke shops that sell WP tobacco in the San Diego area; (3) our preliminary unpublished WP data; and (4) brands most served at 5 WP lounges. We will use a popular flavor 'Double Apple' for all WP smoking sessions as reported in the literature and by our unpublished data (Appendix L. Preferred WP tobacco Flavors & Brands – unpublished data).

Waterpipe Charcoal Protocol and brand - Three Kings quick-light charcoal (40mm): Quick-light charcoal is manufactured to light fast and has been used in previously published studies in naturalistic and laboratroy settings. A standardized protocol will be used in lighting and placing the charcoal on the tobacco-covered head. Three Kings quick-light charcoal (Holland) is an internationally recognized brand, and customarily sold where WP tobacco is sold in Smoke shops and Middle Eastern markets in the U.S. and online. Smokers use them for convenience, since lighting only requires a match or lighter held to it for a few seconds with only a small flame, and usually stay lit up throughout the smoking session.

Questionnaires, Diaries, Forms will be developed based on our previous WP studies.

Screening Form (face-to-face intercept interviews) will collect the name, e-mail address, telephone number, age, gender, smoking habits, and willingness to participate in the study. The RAs will request permission to contact them by phone to confirm eligibility using the inclusion and exclusion criteria. Consent Form is explained in detail in the 'Protection of Human Subjects form'. Tobacco Use History Questionnaire (face-to-face interview using a standardized protocol) Past 7 and 30 days use; average number of cigarettes and/or WP heads and length of time smoked per typical work and nonwork day; past 7 and 30 days secondhand exposure, e.g. average number of WPs and/or cigarettes exposed to per day at home, at work and elsewhere. Exposure will be defined as "in the same room or car with someone who has at least one puff of a cigarette or WP." WP tobacco and charcoal brands use (point of purchase, cost/gram, preferred brands and flavors and reasons for preference). Location at which most often smoked WP at home. Demographics: gender, age, race, ethnicity, age of initiation of WP use and any other tobacco product, education, income, family size and number smokers; height and weight measurement for Body Mass Index calculation (BMI = weight [kg]/height squared [m²]). Illness and Medical Care History Form (face-to-face interview), family history of pulmonary and cardiovascular diseases, cancer, lifetime and past year tobacco-related symptoms, e.g. headaches, dizziness; past year frequency of emergency room, hospitalization & other health services utilization. The 2 following forms will be used for the 3 WP smoking sessions: 7-Day Tobacco Use and Exposure Diaries (Self-administered), a 7-day 24-hour time-diary for participants on frequency, length of time and # of WP heads and/or other tobacco products smoked/exposed to indoors/outdoors by location: home/other location. WP Smoking Session Day & Exposure Form (Self-administered, RAs will complete the WP observation section), frequency, length of time and number of WPs smoked or exposed to indoors/outdoors. Location of smoking: inside home/on patio. Overall description of house: number of rooms, ventilation, windows opened, apartment/house. For WP sessions 2 and 3, open-ended questions on experience, attitudes towards and intention to future use of ice cubes in WP jar and/or use of the charcoal-free electric WP head.

Exhaled Carbon Monoxide (CO) Concentrations. We will measure CO exposure using a Micro+ Smokerlyzer® CO monitor for exhaled CO two minutes before lighting the charcoal and 2 minutes at conclusion of each smoking session. CO is a smoke toxicant that reduces the blood's ability to transport oxygen to various organs, including the brain, and can cause dizziness, headache, syncope and nausea. An acute increase in exhaled CO/COHb, and CO poisoning were demonstrated in WP smokers. Post 50 minutes of smoking, mean expired-air CO concentration increased to 32.9 ± 2.7 ppm in WP smokers, and to 7.4 ± 0.5 ppm when smoked cigarettes.

Urinary Biomarkers of Exposure to Waterpipe Tobacco Smoke. Urinary cotinine, NNAL, SPMA, and 1-HOP, will be determined in WP tobacco smokers to assess comparative risk related to WP tobacco smoking across 3 configurations, as shown in Table 1. We expect that this panel of biomarkers will be higher in smokers who add ice cubes in the WP jar; and SPMA and 1-HOP will be lower in smokers who replace charcoal with charcoal-free electric WP head. We will also assess levels of WP smokers' exposure to furan by quantifying its urinary metabolite Furan-BDA-NAL among WP, in which we expect to find an increase post smoking.

Cotinine will be measured as an index of nicotine consumption in WP smokers using emerging WP smoking practices. On average, 70%-80% of nicotine entering the body is converted into its metabolite, cotinine. Daily use of WP tobacco produced a 24-hour mean (95%CI) urinary cotinine level of 785 ng/ml (578-991ng/ml) equivalent to smoking 10

cigarettes/day. Post smoking WP, mean (95% CI) urinary cotinine increased: 11.8 (7.21-19.2) to 55.3 (33.9-90.1) ng/mg creatinine, N=55.

NNAL will be measured as an important tobacco-specific lung carcinogen. In 55 WP smokers NNAL about doubled (2.1-fold) post WP smoking: 1.32 to 2.84 pg/mg creatinine. Higher urinary mean levels (uncorrected) were found in WP smokers in Syria (N=24) [mean (95% CI), 33.0 pg/ml (21.6-50.6 pg/ml)].

SPMA will be measured as an index for exposure to benzene. We found that urinary SPMA levels in 50 WP smokers increased significantly 2.2 times post a home WP smoking event [geometric mean (GM)(95%CI): 0.26 pmol/mg creatinine (0.17-0.41) to 0.58 pmol/mg creatinine (0.40-0.83)]. A crossover study clinical study found that exposure to benzene when smoking WP tobacco was 2.5 times higher than when smoking cigarettes (N=13) [PMA:GM(95%CI)=1.73 μ g/24h (0.76-3.93) vs. 0.695 μ g/24h, p=0.03, respectively].

1-HOP will be measured as an index for exposure to pyrene. Most PAHs are considered genotoxic carcinogens. A crossover study demonstrated that exposure to pyrene when smoking WP tobacco was 1.5 times higher than when smoking cigarettes (N=13), [1-HP: GM (95%CI)=115 pmol/24h (87-150) vs. 81 pmol/24h (66-101), P=0.01, respectively].

Furan-BDA-NAL Furan, a possible human carcinogen (group 2B), is found in processed food, pollution, car exhaust, and cigarette smoke. The contribution of canned and processed foods to furan exposure is about $0.3 \,\mu\text{g/kg/day}$. Smokers may be exposed to larger amounts of furan than nonsmokers since cigarette smoke contains significant levels of furan (20-40 μg/ cigarette). Heating of a carbohydrate-rich matrix results in chemical conversions, including sugar caramelization, which may result in generation of furanic compounds. Flavored WP tobacco is typically manufactured through the fermentation of tobacco with molasses and sweetened fruit flavors, when smoked produced the smell of caramelized sugars. Using a smoking machine, furanic compounds were generated during one WP smoking session such as up to 62.3±11 mg of 5-(hydroxymethyl)-2-furaldehyde (HMF).

Furan is oxidized to a reactive α , β -unsaturated dialdehyde, *cis*-2-butene-1,4-dial (BDA), a toxic metabolite of this liver toxicant and carcinogen. It has been determined that there is a strong relationship between Furan-BDA-NAL and smoking. Levels of urinary Furan-BDA-NAL, a BDA derived metabolite of furan, were higher in cigarette smokers relative to those in nonsmokers. We will measure sulfides 2 and 4; sulfoxides 3 and 5 and BDA-NAL: 1 and 6. In small sample sizes (N=5, N=16), furan metabolite sulfoxide 3 ranged from 8.7 to 69 pmol/mg creatinine among cigarette smokers and from 1.4 to 6.5 pmol/mg creatinine, with LOQ of <.02. We will be the first to determine the levels of Furan-BDA-NAL in WP smokers, thereby assessing WP smokers' potential health risks associated with furan exposure.

Laboratory Analyses for the Proposed Urinary Biomarkers.

Dr. [name] laboratory at The Masonic Cancer Center, University of Minnesota, will conduct the following laboratory urine analyses, as described previously: NNAL with a LOQ of 1.672 pg/mL (0.01 pmol/mL), 1-HOP with a LOQ of (0.05 pmol/mL), SPMA with a LOQ of 0.03 pmol/mL, Furan-BDA-NAL with a LOQ of <.02 pmol/mg creatinine). [name] at SDSU will conduct laboratory urine analyses for cotinine with a LOQ of 0.1 ng as described previously; and will conduct laboratory analyses for creatinine for normalization.

Gender Representation. Efforts will be made to recruit equal samples of males and females.

Participants Retention and Incentives. Flexible scheduling for study activities where applicable. Following completion of study activities, a \$75 check issued by SDSU will be mailed to non-smokers, and \$250 to smokers: \$100/smoking session and \$25/ training session. Proration will apply for completed activities.

Study Timeline. (Table 3) In the first 3 quarters of Year 1 we will develop forms and procedure manuals, hire and train staff, pilot test and refine protocols and study measures, and obtain IRB approval. Sequential recruitment of participants, data collection, urine aliquoting, data entry, cleaning and coding will start during the 4th quarter of Year 1, and continue through the end of year 2. We expect we will need about 15 months to complete data collection in naturalistic settings. Data analysis and manuscript preparation will start in year 3. Dissemination of results will start in Year 3.

Table 3. Timeline	1			2	3
Forms Procedures manual development					
Hire and train staff					
IRB approval, pilot testing of data					
collection					
Refine data collection & procedures					
manual					
Recruitment of participants					
Measures:					
Study Questionnaire, Forms & Diaries					
CO concentrations, Urine samples					
Battelle - Laboratory analyses					
Urine aliquoting, shipping samples to labs					
Data processing-coding, entry, cleaning					
Data analysis and manuscript preparation					
Dissemination of Results (continues beyond year		⁻ 3)			

General Statistical Analysis Strategy. [name] will oversee data processing and. Statistical analyses will be determined by Drs. [name], [name], [name], [name] and [name]. Final analyses will be conducted using SPSS and Stata software by [name], [name], and [name]. Type I error rate will be set at α =.05, and corrections for Type I error will be performed as necessary (e.g., Bonferroni). We will begin with a comprehensive descriptive analysis of levels of toxicants, CO, and urinary biomarkers and their distribution in the various smoking configurations. Arithmetic means and standard deviations, geometric means and 95% confidence intervals, medians and 25th and 75th percentiles, and minimum and maximum levels will be computed for each outcome measure, and for uncorrected and creatinine-corrected values of urinary biomarkers. Correlations between biomarkers will be determined by Pearson's r. Measures will be log-transformed as necessary, to control for skewed distribution, the undue influence of outliers, and violations of assumptions for statistical inference. Dependent or independent samples t-tests, as appropriate, will compare pairs of machine smoking configurations, smokers post-session vs. pre-session, and smokers vs. non-smokers. Missing data from the questionnaire will be handled using multiple imputation in Stata.

Aim 1 calls for comparing pre/post session change in exhaled CO, and in urinary levels of cotinine, NNAL, SPMA, and 1-HOP in first morning urine samples the morning of, and the morning after, each of 3 WP smoking sessions at home: (Session 1) using charcoal to heat the tobacco and only water in the jar; (Session 2) using charcoal to heat the tobacco and adding ice cubes in the jar; and (Session 3) using electrically heated tobacco and only water in the jar. Among smokers, differences in pre/post change on CO and each biomarker between sessions 1 & 2, and between sessions 1 & 3, will be assessed by mixed regression models to handle repeated measures on each participant. Demographics, duration of smoking, and possible confounding factors, such as number of smokers inside the home and years smoked, will be included as covariates.

Power analysis. As no data exist on effect sizes of differences between session configurations for Aim 2, in Table 4 we show estimated power to detect difference for a range of potential intra-class correlations (ICC) and an effect size of .40 (medium by Cohen's criteria), based on paired z-test, n=50, two-sided alpha=.05. Estimates are conservative, since addition of covariates and adjustment for pre-session CO or urinary biomarker levels in the analyses will increase power.

Table 4. Power				
estimate	es			
Effect	ICC	Darran		
Size	icc	Power		
0.40	0.25	0.637		
0.40	0.50	0.807		
0.40	0.75	0.979		

Aim 2 will examine levels of urinary Furan-BDA-NAL following the analysis strategy described in Aim 1, but using data only from Session 1, the configuration commonly practiced in naturalistic settings, using charcoal to heat the tobacco, and room temperature water in the jar. We will begin with a comprehensive descriptive analysis of demographics and Furan-BDA-NAL levels and their distribution in WP smoker participants. As in Aim 1, analyses will identify differences in metabolite levels between smokers vs. non-smokers, and between pre vs. post WP smoking Session 1, for the sample overall as well as by demographic categories (age, gender, BMI). Pearson's correlations will be conducted between urinary levels of Furan-BDA-NAL and values of other metabolites (cotinine, NNAL, SPMA, and 1-HOP) quantified for WP smoking Session 1.

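### All smokers use the three configurations in one fixed order, so neither Aim 1 contrast can be separated from session order

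*Combined protocol and SAP*

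**What the plan says.** The design is repeated measures in 50 smokers. The sequence is the same for everyone: "Week 1-Session 1, WP smokers will smoke using 1 quick-light charcoal and room temperature water in the WP jar, Week 2-Session 2" with ice added, a training visit in week 3, and the electric head with water in week 4. Table 1, the session descriptions and Aim 1 all give this order.

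Aim 1 defines its comparisons by session number: "Among smokers, differences in pre/post change on CO and each biomarker between sessions 1 & 2, and between sessions 1 & 3", analysed with mixed models. The covariates are demographics, duration of smoking and possible confounders such as years smoked and number of smokers in the home. No period or order term is listed.

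Other provisions bear on the point:

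- Washout: "smokers will abstain from smoking and exposure to any tobacco smoke for 7 days prior to each smoking session". Each session has its own pre-session measurement.
- Smoking Protocol: "participants will be asked to smoke one WP tobacco head at their home as they normally do".
- Tobacco: one package per participant serves all three sessions and the training session. "Following opening the package for session 1, the RAs will place the package in a sealed Ziploc bag".
- Training: "Any day during the third week, the RAs will arrange to visit the participants to train them on the charcoal-free electrically heated WP head".
- Expected result for ice: "We expect that this panel of biomarkers will be higher in smokers who add ice cubes in the WP jar". For the electric head, only SPMA and 1-HOP are expected to fall.
- Non-smokers give urine on two consecutive days only.

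**The concern.** Configuration and session order are the same variable in this design. The difference between sessions 1 and 2 is the ice effect plus whatever else changed between a first and a second study session. The difference between sessions 1 and 3 is likewise the electric-head effect plus three weeks of study participation.

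Washout and the pre/post change handle differences in starting level and limit carry-over. They do not handle a change in how much exposure one session produces, and the plan leaves room for such a change. Smoking intensity is free. Participants use a supplied device with research assistants present and may settle into it. The tobacco ages after the package is opened.

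The ice contrast is the harder one to interpret. The predicted result, a rise in the whole panel, is also what a general rise in smoking intensity from session 1 to session 2 would produce. For the electric head, cotinine and NNAL could serve as a partial check because no fall in them is predicted, but no such check is pre-specified.

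Comparing configurations is the whole of Aim 1. Drift in response would be reported as a configuration effect, or would hide one, and nothing in the data could show which.

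**Working it through.** **1. Reproduce Table 4.** Inputs from the Power analysis section: paired z-test, n = 50, two-sided alpha 0.05, effect 0.40 SD, ICC 0.25, 0.50 and 0.75.

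Standard error of the contrast = √(2(1 − ICC)/50), and power = Φ(0.40/SE − 1.96).

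At ICC 0.50, SE = √(1/50) = 0.1414, and 0.40/0.1414 = 2.828, so power = Φ(0.868) = 0.807. The three ICCs give 0.637, 0.807 and 0.979, which match the table. The arithmetic is sound, but it treats any session difference as a configuration effect.

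**2. Check the aliasing.** Build a design matrix with one column per smoker, two for configuration and two for session position.

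| Design | Columns | Rank |
|---|---|---|
| Fixed order, 50 smokers | 54 | 52 |
| Six orders, 8 or 9 smokers each | 54 | 54 |
| Charcoal sessions swapped 25/25, electric last | 54 | 53 |

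Under the fixed order both configuration contrasts are lost once position is allowed for. Swapping only the charcoal sessions recovers the ice contrast but not the electric one.

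**3. Effect of response drift (drift sizes assumed).** Replace 0.40 in step 1 by the drift, with no true effect, and count both tails:

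| Drift (SD) | ICC 0.25 | ICC 0.50 | ICC 0.75 |
|---|---|---|---|
| 0.1 | 8.9% | 10.9% | 17.0% |
| 0.2 | 21.1% | 29.3% | 51.6% |
| 0.3 | 41.0% | 56.4% | 85.1% |

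A drift of 0.113, 0.092 or 0.065 SD (ICC 0.25, 0.50, 0.75) is enough to double the error rate to 10%. With a true effect of 0.40 SD and an opposing drift of 0.20 SD, the net difference is 0.20 SD, so power at ICC 0.50 is 0.293 instead of 0.807.

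**4. Age of the tobacco.** Taking each session on day 7 of weeks 1, 2 and 4 gives study days 7, 14 and 28. The package is then 0, 7 and 21 days old at sessions 1, 2 and 3.

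**5. Performance of the fix.** Simulation: 20,000 runs, ICC 0.50, no true effect, drift of 0, 0.1 and 0.3 SD at the first, second and third session.

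| Design | Ice contrast rejects | Electric contrast rejects |
|---|---|---|
| Fixed order | 10.8% | 55.3% |
| Six orders with position term | 4.8% | 4.8% |

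With 8 or 9 smokers per order, the contrast variance is 1.000 to 1.0012 times that of the fixed order. Power for 0.40 SD from the t-test is 0.799 (96 df) against 0.800 (98 df).

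For the 25/25 charcoal swap with electric last, under a drift of 0, 0.2 and 0.2 SD, the ice contrast rejects in 4.6% of runs but the electric contrast still rejects in 23.5%.

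**The case against.** Five arguments can be made for the plan as it stands.

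- **The percentages are hypothetical.** They are Table 4's power curve read at assumed drifts and would apply to any fixed-order study of this size. This is true: they show sensitivity to drift, not that drift occurs. The aliasing does not depend on them.
- **Multiplicity correction is allowed for.** The General Statistical Analysis Strategy mentions corrections such as Bonferroni. If all 5 outcomes × 2 contrasts were corrected (alpha 0.005; the plan names no family), the ICC 0.50 rates for 0.1, 0.2 and 0.3 SD become 1.8%, 8.2% and 24.6%. These are lower, but the nominal rate is then 0.5%, so inflation remains.
- **Drift is restrained.** Tobacco weight, brand, charcoal, water and device are standardised, hoses are new, the opened package is sealed, and participants already smoke waterpipe at home. Duration of smoking is a planned covariate and may mean session length. These measures narrow the sources of drift, but puffing stays free. Configuration may itself change session length, or the recorded weight of remaining tobacco, so adjusting for either does not replace balancing the order.
- **The fix is not perfect for drift by calendar week.** If the training week moves with the electric session, the mean session week over the six orders is 2.5 for charcoal with water, 2.5 for ice and 3.0 for electric. A linear weekly drift would leave half a week of bias in the electric contrast, against three weeks (4 − 1) now. This stands as a limit. It does not touch the ice contrast.
- **Aim 2 loses something.** With six orders, charcoal with water would follow another study session in about two thirds of smokers. This is a real cost, and it should be stated.

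**Conclusion.** The concern holds and should be fixed before recruitment. Both Aim 1 contrasts identify configuration effects only if the response to smoking does not drift across sessions. The plan does not state that assumption, and the design cannot test it. No later analysis can repair this, because order and configuration coincide in every smoker.

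This is a failure of identification, not proof of bias: the documents allow neither the size nor the direction of any drift to be worked out. If drift is present, a small amount matters. About 0.09 SD at ICC 0.50, under a quarter of the planned 0.40 SD effect, doubles the uncorrected error rate. Those figures rest on Table 4's test and on assumed drifts. Aim 2's pre/post comparison within Session 1 does not depend on the order.

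**What to change.** Randomise each smoker to one of the six orders of the three configurations, with 8 or 9 per order, and let the training week move with the electric session. Add session position as a fixed effect to the Aim 1 mixed model. Define the Aim 1 contrasts, and the samples for Aim 2, by configuration (charcoal with water). Aim 2 is currently described as "but using data only from Session 1, the configuration commonly practiced in naturalistic settings".

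State the limits that remain: training and the longer gap before the electric session stay part of that configuration under any order, and the usual-practice session used for Aim 2 will often not be the first.

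At minimum, randomise which charcoal session comes first (25/25), include a position term, and report the electric contrast as confounded with session order.

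The cost is a randomisation list, an amendment to the protocol and IRB wording, some extra scheduling and 2 degrees of freedom.
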